	Appendix 9: Medication Adherence Platform6	

# 1. SYNOPSIS

**Protocol Title:** Randomized double blind (sponsor unblind) study evaluating the effect of 14 days of treatment with danirixin (GSK1325756) on neutrophil extracellular traps (NETs) formation in participants with stable chronic obstructive pulmonary disease (COPD)

**Short Title:** Randomized study evaluating the effect of danirixin on neutrophil extracellular traps (NETs) in COPD

#### **Rationale:**

Danirixin (DNX) is a potent selective CXC chemokine receptor type 2 (CXCR2) antagonist being developed as a potential anti-inflammatory agent for the treatment of chronic obstructive pulmonary disease (COPD) and influenza. Clinical pharmacology studies in healthy volunteers demonstrated the pharmacodynamic activity of danirixin (inhibition of *ex vivo* chemokine (C-X-C motif) ligand 1 [CXCL1]-induced CD11b expression on peripheral blood neutrophils and inhibition of neutrophil trafficking after ozone challenge). The current study is a mechanistic study to evaluate the effect of danirixin on neutrophil extracellular traps (NETs) formation. NETs consist of decondensed chromatin coated in antimicrobial and granular proteins. Whilst NETs can have a protective role against bacterial dissemination, excessive NET formation can cause host tissue damage, and could form one mechanism for disease progression in COPD. This study specifically aims to test the hypothesis that danirixin may reduce NET formation (NETosis) in participants with COPD; this study will help to better understand the pharmacology of danirixin and is the first study of its kind in COPD.

Objectives	Endpoints
Primary	
• To assess the change from baseline in NETs formation in participants with COPD following 14 days treatment with danirixin hydrobromide (HBr) 35mg twice daily	• Reduction in sputum NETs (quantified by Histone-elastase complexes)
Secondary	
• To assess the change from baseline in NETs formation in participants with COPD following 14 days treatment with danirixin HBr 35mg twice daily	
 
Reduction in sputum NETS (quantified by Deoxyribonucleic acid [DNA]-elastase complexes)
 
Reduction in sputum NET area quantification by microscopy
 

• To further characterize the safety of danirixin HBr 35mg twice daily compared with placebo in	

Adverse events

Vital Signs

ECG

#### **Objectives and Endpoints:**

	En la state
Objectives participants with COPD	Endpoints
Funder Funder and Constant	
 
Spirometry
 
Clinical Laboratory Assessments (hematology, clinical chemistry,
 

	urinalysis)
• To assess the effects of danirixin HBr 35mg twice daily on NETosis-	• Change from baseline in sputum resistin levels
associated biomarkers in sputum and peripheral blood	• Change from baseline in the ratio of sputum NETs to sputum neutrophils
	• Change from baseline in sputum elastase activity
	• Change from baseline in peripheral blood neutrophil NET formation (DNA release, microscopy)
• Characterise the population pharmacokinetic (PK) profile of approximately 14 days of dosing of danirixin HBr 35mg twice daily in participants with COPD	• Model specific PK parameters of danirixin (e.g., oral clearance, oral steady-state volume of distribution).

Further exploratory analyses related to the above endpoints may be performed.

#### **Overall Design:**

This is a double blind (sponsor unblind), parallel group study, with two groups randomized to 14 days of treatment with either danirixin 35mg HBr or matching placebo. The target population will be individuals with COPD who have evidence of existing elevated sputum NETosis.

There will be no Independent Data Monitoring Committee.

#### Number of Participants:

Approximately 50 participants will be screened to randomize 24 evaluable participants (18 in the treatment arm and 6 in the placebo arm). If a subject prematurely discontinues the study or is unable to complete all study assessments, additional subjects may be enrolled as replacement subjects at the discretion of the sponsor in consultation with the investigator. Additional subjects may be enrolled to improve the statistical properties of the end of study decision criteria (i.e., the probability of a positive outcome) based on the observed variability at an interim analysis. It is expected that the dropout rate in the study should be <10% given the study duration. Enrolment is not expected to exceed a maximum of 32 participants.

#### **Treatment Groups and Duration:**

The study will consist of a screening/baseline period of up to 30 days, a 2 week treatment period, and a 1-week follow-up visit. The study duration, including screening and follow-up, is not expected to exceed 2 months for participants in the study.

Study treatment will consist of two groups: danirixin 35mg HBr orally twice daily or matching placebo.

# 2. SCHEDULE OF ACTIVITIES (SOA)

Procedure	Procedure Pre-Scree and Scree			tment Po (14 days		Follow-up Phone call	Unscheduled visit 	Notes
	V 0	V1	V2	V3	V 4	V5		
Day	Day -30	to -1	D 1	D 7	D14	D 21	As required	
Assessment window				±1d	±1d	± 3d	As required	
Written, informed consent	Х							
Inclusion and exclusion criteria	Х							Recheck clinical status before randomization.
Demography, Medical history	Х							
Baseline COPD assessment test (CAT) score	Х							
Adverse event (AE)/Serious adverse event (SAE) review	Х	+	-=====	======	$\rightarrow$	Х	Х	
Concomitant medication review	Х	←			$\rightarrow$	Х	Х	
Full physical examination including height and weight	Х						Х	
Vital signs	Х	Х	Х	Х	Х		Х	
Volatile organic compound (VOC) measurement	Х3	X 	X5	X3	X3		Х	
Spirometry	Х		Х		Х		Х	
Induced Sputum Samples (including biomarker samples)	Х	X 4	Х	Х	Х		Х	
Spirometry post-Sputum Induction	Х	X 4	Х	Х	Х		Х	
Triplicate 12-lead ECG		Х	Х		Х		Х	
Chest X-ray (historical within 1 year acceptable)		Х						
HIV, Hepatitis B and C screening		X6						
Laboratory assessments (clinical chemistry including liver chemistries, haematology, biomarkers)		х	Х		х		х	
Pharmacokinetic (PK) sample			X7	X8	X7		Х	See footnotes for timings of PK sampling
Genetic sample			Х9					Pre-dose (baseline) sample.
Urinary Pregnancy test (WOCBP only)		X 	X 		X 		X 	
Urinalysis (including biomarker samples)		Х	Х		Х		Х	
Randomization			Х					All baseline assessments at V2 should be completed prior to randomization
Study treatment			Х	$\leftrightarrow$	Х			

#### CONFIDENTIAL

Procedure	Pre-Screening and Screening 						Follow-up Phone call	Unscheduled visit 	Notes
	V0	V1	V2	V3	V 4	V5			
Dispense study medication			Х						
Monitor IP compliance (via manual counting and App)			Х	Х	Х			Digital App monitoring to begin at V2	
Collect IP					Х				

• The timing and number of planned study assessments, including safety, pharmacokinetic, pharmacodynamic/biomarker or other assessments may be altered during the course of the study based on newly available data (e.g., to obtain data closer to the time of peak plasma concentrations) to ensure appropriate monitoring.

- Any changes in the timing or addition of time points for any planned study assessments must be documented and approved by the relevant study team member and then
  archived in the sponsor and site study files, but will not constitute a protocol amendment. The IRB/IEC will be informed of any safety issues that require alteration of the safety
  monitoring scheme or amendment of the Informed consent form (ICF).
- Safety assessments should be performed in the following order where applicable/ possible: vital signs, ECG measurements, blood samples and spirometry.
  - Screening visit is split into pre-screening on visit 0 and screening on visit 1 although the visits may be performed on the same day. This is to a) enable participants to
    potentially have more than one attempt at sputum induction for meeting eligibility and b) to only collect minimal screening data for subjects who fail on the basis of the elevated
    NETs since that is the key inclusion criteria that may not be known from medical records.
  - 2. Unscheduled visits may be used to collect information related to adverse events, for follow up of any safety assessments, and also to complete assessments where participants were not able to perform these within the visit window for any reason. It is not necessary to carry out all of the assessments listed under an unscheduled visit at a single visit; the assessments performed should be driven by the need for the visit.
  - 3. VOC measurement should be undertaken prior to sputum induction at these visits.
  - 4. Sputum induction (and associated VOC measurement and safety spirometry) at visit 1 is only necessary if participant unable to give sample at visit 0. Where the participant is judged by the investigator to have a borderline sputum NETs level (<0.5 units/ml) at visit 0, they will be invited to give a second sputum sample on visit 1 to re-assess eligibility.

  - 5. VOC measurements should be undertaken at the following timepoints at this visits: prior to sputum induction, and 4 hours post dose
  - 6. Hepatitis B (HBsAg) and Hepatitis C (HepC antibody) testing is required. If testing otherwise performed within 3 months prior to the first dose of study treatment, testing at screening is not required. Hepatitis C Ribonucleic acid (RNA) testing is optional; however a confirmatory negative Hepatitis C RNA test must be obtained, to be able to enroll participants with positive Hepatitis C antibody due to prior resolved disease.
  - 7. At visits 2 and 4, PK samples should be collected at the following time-points: pre-dose, 0.5, 1, 2 and 4 hours post-dose.
  - 8. At visit 3 only a pre-dose PK sample should be collected.
  - 9. Agreeing to genetic sample consent is not required for overall study participation. Informed consent for genetic sample must be obtained prior to taking sample.
  - 10. Pregnancy testing only required for women of child bearing potential (WOCBP). A positive urine pregnancy test requires confirmation with a serum pregnancy test.

# 3. INTRODUCTION

The inflammation associated with chronic obstructive pulmonary disease (COPD) is characterized by a prominent infiltration of neutrophils in lung tissue and the airways. Neutrophils and other inflammatory cells are recruited to the lung in response to various chemotactic factors, including chemokines. Specifically, there is a large body of evidence that the CXC chemokine receptor type 2 (CXCR2) chemokine receptor plays a pivotal role in neutrophil recruitment to the lung. For neutrophils, chemokine binding to the CXCR2 receptor results in chemotaxis and cell activation, ultimately resulting in the release of a number of inflammatory mediators and proteases that are thought to contribute to the progressive fibrosis, airway stenosis, and destruction of the lung parenchyma characteristic of COPD.

Danirixin is a selective CXCR2 antagonist being developed as a potential antiinflammatory agent for the treatment of COPD and influenza. Danirixin has demonstrated potent antagonism of CXCR2 activity both *in vitro* and *in vivo* in preclinical studies [GlaxoSmithKline Document No. YM2010/00163/08].

Clinical pharmacology studies in healthy volunteers demonstrated the pharmacodynamic activity of danirixin (inhibition of *ex vivo* CXCL1-induced CD11b expression on peripheral blood neutrophils). In a Phase IIa study in symptomatic participants with mild to moderate COPD at risk for exacerbation (GSK Study No. 200163) [GlaxoSmithKline Document No. 2013N180289\_03], danirixin reduced respiratory symptoms as measured with E-RS:COPD, compared to placebo [Miller, 2016].

## 3.1. Study Rationale

The aim of this study is to better understand the mechanism of action of danirixin, and to understand whether danirixin impacts neutrophil function via effects on neutrophil extracellular traps (NETs) formation in sputum and in peripheral blood *in vivo*, since *in vitro experiments* have suggested that CXCR2 antagonism reduces NETs formation in peripheral blood neutrophils from COPD patients [Pedersen, 2017], with NETs formation being proposed as one mechanism for disease progression in COPD.

This study specifically aims to test the hypothesis that twice daily administration of danirixin HBr 35mg reduces NET formation in participants with COPD and is the first study of its kind in COPD. Reduction of NET formation has potential application in a host of chronic lung diseases, infections and autoimmune disease, thus supporting development of danirixin across a wide range of indications.

## 3.2. Background

Danirixin is being evaluated as an addition to standard of care inhaled therapies (i.e. long acting bronchodilators and long acting bronchodilator/corticosteroid combination therapies) and is targeting those COPD patients that continue to have a burden of respiratory symptoms and COPD exacerbations despite management with currently available COPD treatments. There is a paucity of novel therapies that target these symptoms, and there are no currently available therapies that modify disease progression

#### CONFIDENTIAL

in COPD. There are no licensed CXCR2 antagonists currently available, with one other compound (AZD5069) currently under development for indications other than COPD.

The current study is a mechanistic study to better understand the pharmacology of danirixin and to assess the effect of danirixin on neutrophil extracellular traps (NETs) formation (or NETosis). NETs consist of decondensed chromatin coated in antimicrobial and granular proteins that are extruded in the extracellular space by neutrophils as a defensive mechanism in response to microorganisms, soluble factors and host molecules [Pires, 2016].

Whilst NETs can have a protective role against bacterial dissemination [Brinkmann, 2004] excessive NETosis can cause host damage, with the lung being especially vulnerable to damage from NETs. For example, following infection with the H1N1 virus in animal models, NETs expressing MMP-9 were found entangled with alveoli, causing increased alveolar capillary damage and small airway obstruction, suggesting a link between these DNA lattices and lung damage [Narasaraju, 2011]. There is differential activation of NETosis pathways and responses in reaction to different pathogens and triggers [Delgado-Rizo, 2017] hence consideration of both the host microbiome and infectious species are important. COPD patients colonized with *Haemophilus Influenzae* appear more susceptible to NETosis [Dicker, 2017], therefore identification of host microbiome subspecies could be important for targeting patients for treatment with CXCR2 antagonists. Detection of the lung microbiome has been explored via breath analysis of volatile organic compounds (VOC), and may provide a non-invasive method to identify people with COPD who are colonized with *Haemophilus Influenzae* [Shafiek, 2015]

In addition to infectious disease, massive NET formation has also been reported in autoimmune diseases, inflammatory disease, and several lung diseases [Delgado-Rizo, 2017], including COPD, and could form one mechanism for disease progression [Grabcanovic-Musija, 2015; Dicker, 2017].

Blocking CXCR2 on neutrophils has been shown to decrease NET formation in some inflammatory *in vitro* and murine models [Marcos, 2010]. In peripheral blood neutrophils derived from COPD patients, in vitro treatment with CXCRs antagonists showed a reduction in NETs formation [Pedersen, 2017].

This study specifically aims to test the hypothesis that danirixin may reduce NET formation (NETosis) in participants with COPD, to improve our understanding of its pharmacology in humans, and the definition of target patient population for subsequent clinical trials.

A detailed description of the chemistry, pharmacology, efficacy, and safety of GSK1325756 is provided in the Investigator's Brochure.

#### 3.3. Benefit/Risk Assessment

More detailed information about the potential benefits and risks of danirixin may be found in the danirixin Investigator's Brochure [GlaxoSmithKline Document No. YM2010/00163/08].

#### 3.3.1. Risk Assessment

Potential Risk of Clinical Significance	Summary of Data/Rationale for Risk	Mitigation Strategy
	Investigational Product (IP) GSK 1325756	
Testicular effects and male fertility	The most sensitive species is the rat. Testicular effects present at doses ≥150 mg/kg/day in the rat include spermatid degeneration, seminiferous tubular degeneration and secondary epididymal changes, including oligo/aspermia and/or epididymal intratubular cellular debris. The no observed adverse effect level (NOAEL) in this study, based on the microscopic findings in the testis, was 50 mg/kg/day for male rats. The systemic exposure margins for the NOAEL for testicular effects in the rat is 7.3-fold for an oral clinical dose of 50 mg twice daily dosing (BID) free base tablet. The testicular effects seen in the rat have also been shown to directly impact on male fertility and the NOAEL for these reproductive effects was 100 mg/kg/day. Refer to IB Section 4.4 for full details No adverse events related to testicular effects have been observed in clinical studies to date.	Standard safety monitoring will be employed. The potential risk of testicular injury has been conveyed in the informed consent. PK modelling predicts that in a participant receiving 35 mg BID of the HBr salt, the risk of exposure exceeding the 2-fold margin for area under the concentration curve from pre-dose to 24 hours post-dose (AUC[0-24] for the NOAEL of testicular effects is low.
Impairment of host defense.	Host defense has not been studied directly in nonclinical studies. However, data in nonclinical species have not identified an increased risk of infection with danirixin. Nonclinical studies in mice and ferrets with two CXCR2	Monitoring of peripheral blood neutrophil count. Stopping criteria: in participants with a
	antagonists in the same chemical class as danirixin have not shown an increase in infections in challenge models	confirmed absolute neutrophil count $\leq 0.5 \text{ x}$ $10^9/\text{L}$ product will be discontinued and

Potential Risk of Clinical Significance	Summary of Data/Rationale for Risk	Mitigation Strategy
	(e.g., influenza viral load).	neutrophil count will be monitored until return to normal.
	Secondary bacterial infections after viral	
	infection have not been directly evaluated in nonclinical studies.	Ongoing assessment of AE/SAEs related to infection. Closely monitor, collect information on and characterize infection
	The data from clinical studies including healthy participants, COPD and influenza patients thus far show no evidence that	events such as pneumonia, and use adjudication as appropriate.
	participants taking danirixin have an increased infection rate compared with participants taking placebo.	
	Neutropenia has been reported in clinical trials of other CXCR2 antagonists. No instances of neutropenia have been reported in nonclinical studies with danirixin. In healthy volunteer studies and a phase 2a study in patients with Influenza (GSK Study 201682, GlaxoSmithKline Document No. 2014N205875 00), decreased neutrophil	
	counts have been observed in subjects receiving either placebo or danirixin; no instances of danirixin-related neutropenia have been reported in clinical studies to date. In healthy subjects, the data are confounded by the	
	observation of low neutrophil counts before dosing or at follow-up, and were not dose-related, while in patients with influenza, neutrophil counts recovered while receiving danirixin, coincident with resolution of the viral infection.	
	There have been no reports of neutrophil count decreases below the lower limit of normal in patients with COPD	

Potential Risk of Clinical Significance	Summary of Data/Rationale for Risk	Mitigation Strategy						
	who were treated with danirixin for one year.							
	These data support the conclusion that a causal association of neutropenia with danirixin cannot be definitively established.							
Reproductive toxicology (Embryofetal development)	In a rat embryofetal development study, an oral dose of 300 mg/kg/day resulted in fetal skeletal variations in the skull (reductions in ossification). There were no test article elated effects on numbers of corpora lutea, implantations, embryofetal survival, placental morphology, gravid uterine weight, sex ratio, fetal body weight, or fetal morphology (external and visceral).	As danirixin HBr has shown the potential to cause fetal malformations, danirixin or danirixin HBr must not be administered to pregnant women or nursing mothers. Women of childbearing potential should only be included in clinical trials with the use of appropriate precautions against pregnancy. Male participants with female partners of child-bearing potential must comply with the contraception requirements.						
	Study Procedures							
Sputum Induction	During induction of sputum, the hypertonicity of saline, the rate and volume of administration can potentially cause bronchoconstriction and clinically important dyspnoea in some patients with COPD, with a resulting fall in forced expiratory volume in one second FEV 1 of >10%.	Participants will be dosed with bronchodilators prior to sputum induction and will have a post-induction spirometry measure at 15 minutes, and will be treated with bronchodilators if there is evidence of bronchospasm.						
	Other							
None								

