# 5. STUDY DESIGN

## 5.1. Overall Design

[figure not shown]
A study schematic is shown in Figure 1. This is a parallel group study. Following screening, participants will be randomized (3:1) to receive danirixin 35 mg or placebo. Study treatment will be administered twice daily for 2 weeks.

Based on the observed variability at an interim analysis, additional subjects may be enrolled to improve the statistical properties of the end of study decision criteria (i.e., the probability of a positive outcome). Outputs containing unblinded treatment assignments will be created for this interim analysis will only be made available to a limited number of GSK staff. Full details will be included in the study data dissemination plan. No Independent Data Monitoring Committee (IDMC) will be utilized for this study.

While the study is being conducted, core members of the study team will be unblinded (with the exception of those study team members who will directly interact with study sites, e.g. Operations and Science Leader and Data Quality Leader). There will be ongoing review of safety data and clinical outcomes. Only the study statistician will have access to individual participant treatment assignments, other core team members will review aggregate summaries by study treatments. A study charter will specify which team members will have access to unblinded data while the study is ongoing and the data to be included in the data reviews.

The danirixin safety review team will perform ongoing safety review and will meet at least once while the study is ongoing and as needed based on emerging data to review available safety information.

• Follow up phone-call to occur within 7 days of last dose of study medication

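### The neutrophil stopping rule has only one scheduled on-study count behind it, at the visit where study drug is collected; adding a Day 7 count would be cheap

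*Protocol*

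**What the plan says.** For impaired host defence, the mitigation column in Protocol Section 3.3.1 begins "Monitoring of peripheral blood neutrophil count. Stopping criteria: in participants with a" and goes on to a confirmed ANC of 0.5 × 10⁹/L or below, at which dosing ends and the count is followed until normal. The same cell adds continuing review of infection-related adverse events. It states no frequency for the counts; Sections 9.4 and 9.4.4 refer to the SoA for timing.

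In the SoA (Protocol Section 2, repeated in SAP Section 12.2.1) the row "Laboratory assessments (clinical chemistry including liver chemistries, haematology, biomarkers" is marked at V1, V2, V4 and unscheduled visits, and is blank at V3 (Day 7) and V5 (a phone call). For V2 the table notes: "All baseline assessments at V2 should be completed prior to randomization". Study drug is collected at V4. V3 is a site visit with a blood draw, for pharmacokinetics: "At visit 3 only a pre-dose PK sample should be collected".

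Section 8.1.2 requires a low count to be confirmed on repeat testing before the participant stops, and refers to Appendix 8 for detail. Appendix 8 calls for immediate discontinuation, a repeat count within 24 hours, daily counts until recovery or stabilisation, and treatment of suspected infection.

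On the size of the risk, Section 3.3.1 says "Neutropenia has been reported in clinical trials of other CXCR2 antagonists", but for this drug "no instances of danirixin-related neutropenia have been reported in clinical studies to date".

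**The concern.** A stopping rule limits a participant's exposure only if its trigger is measured while there is still dosing to stop. Here the one scheduled trigger after the first dose falls at the end of dosing. A participant whose count fell without symptoms during the two weeks would take essentially the whole course before anyone was due to look. What is at stake is the protection of individual participants. The efficacy result does not depend on it.

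**Working it through.** The plan gives no figure to reproduce, so the check is a reading of the schedule followed by a count of doses.

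**Scheduled counts after first dose.** Haematology is marked at V1, V2 and V4. V1 is screening and V2 precedes randomization, so both are pre-dose. V4 alone remains: one count.

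**Inputs for the dose count**
- Two doses a day for 14 days (Protocol Section 5.1); SAP Section 12.6.2 uses 14 × 2 = 28 as the compliance denominator.
- If the last dose is the one taken in clinic at V4, because drug is then collected, the total is 13 × 2 + 1 = 27.
- V3 is Day 7 ± 1 and V4 is Day 14 ± 1 (SoA).
- Doses taken before a pre-dose draw on day d = 2(d − 1).
- Assumptions: the safety draw precedes that day's first dose, and action follows either the same day or 24 hours (two doses) later. Laboratory turnaround is not documented; 24 hours matches the Appendix 8 limit for the repeat count.

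**Results on the 28-dose count**

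| Visit | Day of draw | Doses already taken | Left, same-day stop | Left, stop 24 h later |
|---|---|---|---|---|
| V4 | 13 | 24 | 4 | 2 |
| V4 | 14 | 26 | 2 | 0 |
| V4 | 15 | 28 | 0 | 0 |
| V3 | 6 | 10 | 18 | 16 |
| V3 | 7 | 12 | 16 | 14 |
| V3 | 8 | 14 | 14 | 12 |

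**At V4.** Drug is handed back at this visit, so at most the in-clinic dose is open to prevention, whatever the table leaves arithmetically. That dose is spared only if a same-day result is read before dosing and acted on at once. If the site waits for confirmation, none is spared. The realistic figure is 0 to 1.

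**At V3, if a count were added.** At nominal days on the 28-dose count, 16/28 = 57% (same day) or 14/28 = 50% (24 hours later) could be withheld. On the 27-dose count it is 27 − 12 = 15, or 56%, and 15 − 2 = 13, or 48%. That is about half either way.

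**Sensitivity to visit windows, last dose in clinic at V4.** With V3 late and V4 early, the total is 12 × 2 + 1 = 25 and 25 − 14 = 11 remain (44%). With V3 early and V4 late, the total is 14 × 2 + 1 = 29 and 29 − 10 = 19 remain (66%). A 24-hour lag takes two doses from each: 9/25 = 36% and 17/29 = 59%.

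**Condition on all V3 figures.** They apply only to a participant whose count is already at the threshold on Day 7. The documents give no time course for a fall in neutrophils, so the chance of that cannot be calculated.

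**The case against.** The strongest defence is that nothing here is inconsistent. A reader might infer that Section 3.3.1 promises on-treatment monitoring that the SoA then fails to deliver. The documents do not support that: 3.3.1 gives no frequency, and Sections 9.4 and 9.4.4 leave timing to the SoA, which states it. This part of the defence stands.

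Nor is the V4 count worthless as mitigation. A low value starts daily monitoring, treatment of suspected infection and reporting to the sponsor within 24 hours, and Appendix 8 sets the repeat count within 24 hours, so the confirmation step is not left untimed. This stands too; the V4 count fails only at limiting exposure.

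Participants with symptoms can be tested earlier: the SoA marks laboratory tests for unscheduled visits, and Section 9 and Appendix 2 allow extra samples. But these are need-driven, so an asymptomatic fall has no planned route to detection. The protocol also says "The danirixin safety review team will perform ongoing safety review and will meet at least once while the study is ongoing". That review can use Day 14 counts from earlier participants to protect later ones, but cannot find a fall within a participant during dosing.

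Finally, the documented risk is low. Section 3.3.1 reports no counts below the lower limit of normal in COPD patients treated for one year, and exclusion criterion 17 removes anyone below 1.0 × 10⁹/L at screening. The only adverse signal is from other CXCR2 antagonists, with no rate, depth or timing given. This stands and fixes the point as minor.

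**Conclusion.** The point holds as a minor design weakness. There is one scheduled post-dose neutrophil count, at the visit where drug is collected, and it can spare that participant about 0 to 1 doses. A Day 7 count could leave about half the course (roughly 13 to 16 of 27 to 28 doses at nominal days) open to being withheld, provided the count had already fallen to the threshold by then. A fall after Day 7 would still be found only at V4.

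The figures rest on pre-dose draws, action the same day or 24 hours later, and the two dose-counting conventions shown. It would be wrong to infer that a Day 7 count halves exposure for every participant who becomes neutropenic, or that participants faced a demonstrated hazard; the documents give no time course for the first and report no danirixin-related cases for the second. The primary endpoint is untouched.

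SAP Section 3.2 records that the study stopped early with 19 completers, so the point concerns the protocol as designed and any reuse of this schedule.

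**What to change.** Mark haematology with differential at V3 in the SoA, taken with the existing pre-dose pharmacokinetic draw, and have the result reviewed on receipt against Section 8.1.2 and Appendix 8.

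The cost is one local blood count per participant: about 24 for the evaluable target and at most 32 at the randomization cap in Section 5.2. No new visit or needle-stick is needed, and the small extra volume has to fit the 500 mL limit in Section 9. The downside is an occasional repeat test for a transient low value. The SoA notes provide that added time points, once documented and approved, are "archived in the sponsor and site study files, but will not constitute a protocol amendment".
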